### **11.2 Protocol to ensure confidentiality.**

Each subject will be tracked using an Access database. Each site will have a separate Access database built using the same template. The databases, containing identifiers and other related information for coordinating research activities (recruitment outcome, interview call log and interview visit schedule, etc.) will be kept on the secure Northwestern and Mayo Clinic network drives respectively. Only the PI, project manager, and RCs at each site will have access to this database.

Data will be collected via RedCap. RedCap is a secure, encrypted online data collection tool, which can only be accessed by NU authorized personnel listed on the project's IRB. An affiliate Northwestern Net ID will be generated for the RC at Mayo Clinic to enable data entry for Mayo participants. Data access groups will be identified so NU interviews cannot access to Mayo's data and vice versa.

Several methods will be employed to reduce the risk of breach of confidentiality. A study identification number will be assigned to each subject in the study. The research data collected and stored will have the study identification number and no other identifying information on it. The consent forms and the de-identified study data will be kept in a separate locked file cabinet. Using this method, if someone were to gain illegal access to the locked filing cabinet with study data, they would have no way to link this data to any identifying information.

### **11.3 Quality Assurance.**

Training will begin after surveys and interview protocols have been refined and standardized. A training session will be conducted by Drs. [name] and [name] at each site. The training will include tailored discussion of 1) roles and responsibilities; 2) HIPAA and IRB mandates (completion of Human Subjects Training Program - CITI); 3) effective recruitment communication and interviewing with attention paid to health literacy and culture; and 4) gathering and recording data including administering the structured survey electronically. Role playing will be used to fine tune training for obtaining informed consent and interviewing patients. Institutional Review Board (IRB) approval will be attained at both sites prior to any active recruitment efforts. All interviewers will be required to demonstrate competence in survey administration.

### **11.4 Study-wide data management.**

Data collected includes patient consent forms, data gathered using the EDW and Transplant Report pulls, and data collected during the study interviews.

#### COVID-19 Survey Data

By extending existing studies conducted by [name] (LitCog (STU00026255), REMinD (STU00203777), COPD Multimorbidity (STU00201640), UMS Portal

(STU00201639), and TAKE IT (STU00204465) to capture an additional patient-reported outcome related to one's knowledge, attitudes and behaviors related to COVID-19, we can link participants' responses to this cross-sectional survey to a minimum data set of participant characteristics that include demographic, socioeconomic, cognitive (including health literacy) and health behavioral characteristics. We will then be able to investigate determinants of COVID-19 knowledge, attitudes and behaviors without duplicating data collection efforts for these variables.

*Data Access.* The Data Custodian is the Principal Investigator, [name]. Only authorized personnel listed on each institutions IRB will have access to the data. Any information that could allow identification of individual participants, including the master list, will be kept strictly confidential.

*Local Data Storage.* Data will be stored in REDCap, a secure, web-based application, and on the Northwestern and Mayo Clinic secure servers for the length of the study. RCs at Mayo Clinic will be provided with an affiliate Northwestern id in order to be granted access to NU's REDCap system. RCs will be assigned to their own Data Access Group which restricts access to their subject's records. Each group is blinded to all other data/records. For the purposes of creating a clinic alert notification, intervention patients' name, DOB and MRN will be entered into RedCAP and sent to pre-identified clinical staff via RedCAP survey function to Northwestern email addresses. For Mayo Clinic patients, name, DOB and MRN will also be entered into RedCAP and sent to pre-identified clinical staff via RedCAP to Mayo clinic email addresses. The name, DOB and MRN will be stored in the Mayo Clinic Data Access Group, which will not be visible to any Northwestern staff. Only the RC at the Mayo Clinic will have access to this data in the RedCap Data Access Group.

The Project Manager or Data Analyst will download the de-identified data only for both sites from REDCap monthly and save to the "Analytic" folder within the TAKE IT project folder on the FSM department servers which are located in a HIPAA compliant data center. These data files do not contain any identifiable information, and are identified by project staff by an assigned study ID. All identifiable information for Northwestern patients will remain in the secure REDCap system. Upon completion of all study activities, a final de-identified dataset will be created and all identifiable information will be deleted. This dataset will be stored indefinitely on the GIM server for secondary analyses. Only authorized personnel will have access to the dataset. All identifiable information will be deleted upon completion of the study

*Data Transfer to Data Coordination Site.* All survey data collected at the Mayo Clinic site will be stored in REDCap and downloaded by the Northwestern project manager or data analyst monthly. For the purposes of creating a clinic alert notification, intervention patients' name, DOB and MRN will be entered into RedCAP and sent to pre-identified clinical staff via RedCAP survey function to Mayo Clinic email addresses. The name, DOB and MRN will be stored in the Mayo Clinic Data Access Group, which will not be visible to any Northwestern staff. Only the RC at the Mayo Clinic will have access to this data in the RedCap Data Access Group. Northwestern staff will only have access to de-identified

study data from Mayo Clinic. De-identified data from both sites will be combined into a master dataset. A back-up copy of all transferred data will be maintained at Mayo Clinic.

**12.0 Provisions to Monitor the Data to Ensure the Safety of Participants:**

**12.1 Data Safety and Monitoring Board (DSMB).** The DSMB will be formed early in the project and be given responsibility to review and approve the methods and analysis plan. It will be organized by Drs. [name] and [name] and include appropriate research methodologists and biostatisticians with related expertise. Meetings will be via video/tele-conference to review protocols, procedures, and concerns related to research integrity.

**13.0 Withdrawal of Participants:**

**13.1** In the case that subjects are unresponsive for 6 months past the date their follow up interview was due, they will be labeled as ‘lost to follow up’ and will be withdrawn from the study.

**13.2** Participants can choose to withdraw from the study at any time. If a participant chooses to withdraw from the research, any data collected up until the point of withdrawal will still be utilized as it will not include identifying information.

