### Aim 2.

Generalized linear mixed models (GLMMs) will be used to examine intervention effects over the course of the study. Link functions will be included as described above for the GLM models. Adherence concerns may differ in the two cohorts, thus separate models will be employed for each cohort (de novo, established). Treatment group will be the independent variable of primary interest, modeled as a fixed effect with the usual care group specified as reference group. We will also include fixed effects for site (NU, Mayo), time since transplant (in months), and potential confounding covariates noted in bivariate analyses. Random participant effects for each participant will be included to account for repeated measurements nested within each participant (assuming a compound symmetry, although we will fit autoregressive structures as well, comparing fit using AIC and BIC criterion). Outcomes recorded at each interview will be analyzed by visit whereas adherence measured by tacrolimus levels, along with blood pressure control will be analyzed in 6-month intervals as described above. A time-since-transplant-by-arm interaction term will be included to examine if outcome trajectories/slopes over time differ by study arm. Since prescription knowledge and adherence will be assessed for each medication, 2-level GLMM will be used for these outcomes with medications nested in participants. For  $\Delta$  eGFR and re-hospitalization outcomes, GLM models will be used since outcomes over 2 years are summarized in a single measurement. In the de novo cohort, change in eGFR from transplant to 2 years post-transplant and # hospitalizations (any hospitalization, if rare) within 2 years post-transplant will be modeled. For the established cohort, the time period for the both measures will span from transplant to 2-year study visit. It is possible those who do not complete the 2-year visit will differ in important characteristics (e.g. cognition, comorbidity), which could bias results. We will use collected data at prior interviews to understand the extent that individuals who complete follow-up differ from those who do not. If differences are found, pattern-mixture models will be employed by classifying participants' drop-out type or pattern (e.g. completed, refused, lost to follow up, death). This variable will then be added to mixed effects models to account for differences.

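### Section 13.1 withdraws interview non-responders from the study without preserving EHR follow-up, and the one-year Aim 1 analysis names no method for missing outcomes and gives a conflicting analysed N

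*Combined protocol and SAP*

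**What the plan says.** Section 13.1 sets the trigger: "In the case that subjects are unresponsive for 6 months past the date their follow up interview was due". Those participants are labelled lost to follow-up "and will be withdrawn from the study". Chart review is not mentioned. Section 13.2 deals with a different group: "If a participant chooses to withdraw from the research, any data collected up until the point of withdrawal will still be utilized". No section says whether EHR collection continues for someone withdrawn under 13.1.

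Section 8.4 takes the clinical outcomes from the EHR at each site and tacrolimus levels from routine monitoring. Section 9.1 also names the EHR as a source for adherence and clinical outcomes. Section 25.3 says that written consent includes authorisation to review the medical record.

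Section 11.1, Aim 2, fixes the outcome windows. In the de novo cohort, eGFR change runs from transplant to two years after it, and for hospitalisations the text is "hospitalizations (any hospitalization, if rare) within 2 years post-transplant will be modeled". In the established cohort, "the time period for the both measures will span from transplant to 2-year study visit". For both outcomes, "GLM models will be used since outcomes over 2 years are summarized in a single measurement". Aim 2 also anticipates drop-out: "It is possible those who do not complete the 2-year visit will differ in important characteristics". If differences are found, participants are classified by drop-out pattern, and "This variable will then be added to mixed effects models to account for differences".

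Section 11.1, Aim 1, makes adherence at one year the main outcome. It is analysed by a GLM adjusted for site, time since transplant, the baseline value of the outcome and confounders. Aim 1 expects 90% retention (de novo) and 85% (established), with at least 525 patients for the primary analyses. It names no imputation, no rule for missing outcomes and no sensitivity analysis. The Power Calculation uses 610.

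**The concern.** Not answering interviews and having no medical record are different things. A rule triggered by missed interviews should not end observation of outcomes that need no interview. If 13.1 is followed as written, the end-of-window eGFR is missing. The hospitalisation record is either missing or shorter than the window that Aim 2 defines, and the plan does not say which. If a short record is counted as it stands, unobserved time is treated as event-free. The drop-out variable does not help, because it enters only the mixed models and these two outcomes are analysed by GLM. For established patients there is a further gap however 13.1 is read: their window ends at a visit that a non-responder never attends.

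In Aim 1, patients who stop responding in an adherence trial may also be those who stop taking their medicines. The one-year GLM makes no use of the 6-week, 6-month or EHR data of those lost. Aim 2's check looks at the 2-year visit in separate cohort models, so it does not reach the pooled 12-month contrast.

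**Working it through.** **1. The plan's own figures.** Power Calculation: 305 per arm, 45% against 34% non-adherent, 5% error (two-sided assumed). Power = Φ[(0.11 − 1.96 × √(2 × 0.395 × 0.605/305)) / √((0.45 × 0.55 + 0.34 × 0.66)/305)] = Φ[(0.11 − 1.96 × 0.0396)/0.0393] = 79.5%, in line with the stated 80%.

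Retention: Aim 1's 350 + 350 at 90% and 85% gives 315 + 297.5 = 612.5, close to 610. Table 5's 270 + 340 = 610 matches 300 × 0.90 + 400 × 0.85. But 525/700 = 75%, below both stated retention rates.

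**2. Who is affected.** 700 − 610 = 90 (13%). This is an upper bound on the 610 figure, because it includes deaths, voluntary withdrawals and patients who respond again later. One-year loss is the right base: silence starting at the 18-month interview leads to withdrawal at month 24, when nothing is left to lose.

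**3. Follow-up lost.** Withdrawal month w = interview month + 6. Six weeks is 1.38 months, so w = 7.38, 12 or 18. With e the months from transplant to enrolment and L the window length from transplant, time lost = L − (e + w). The share of the expected count lost is that time divided by L, assuming a constant event rate. De novo: e = 1.38 (Section 5.2 identifies Mayo de novo patients at 6 weeks), L = 24. Established: L = e + 24, with e = 12 and e = 24 as illustrations.

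| Silent from | De novo | Established, e = 12 | Established, e = 24 |
|---|---|---|---|
| 6 weeks | 15.2 months, 63.5% | 16.6 months, 46% | 16.6 months, 35% |
| 6 months | 10.6 months, 44% | 12 months, 33% | 12 months, 25% |
| 12 months | 4.6 months, 19% | 6 months, 17% | 6 months, 12.5% |

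If events cluster soon after transplant, the shares are smaller.

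**4. Effect on an arm's count.** Share × 90/700: from 12.5% × 0.1286 = 1.6% to 63.5% × 0.1286 = 8.2%. The top end needs every lost patient to be de novo and silent from the 6-week call.

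**5. Effect between arms.** Assume 90% retention in one arm and 85% in the other; the plan gives these as cohort rates, not arm rates. Count ratio = (1 − 0.10 × share)/(1 − 0.15 × share). At 12.5% this is 0.9875/0.98125 = 1.006; at 63.5% it is 0.9365/0.9048 = 1.035. With equal retention and timing it is 1.

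**6. eGFR.** Recovering all 90 would move Table 5's detectable difference from 2.9 to 2.9 × √(305/350) = 2.7 at best. Table 5 already allows for the loss.

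**7. Aim 1.** Assume no true effect, 45% non-adherent overall, a proportion p non-adherent among those lost, and retention r. Non-adherence among completers = (0.45 − (1 − r) × p)/r.

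| p | r = 0.90 | r = 0.85 | False difference |
|---|---|---|---|
| 0.6 | 43.3% | 42.4% | 1.0 points |
| 0.7 | 42.2% | 40.6% | 1.6 points |
| 0.8 | 41.1% | 38.8% | 2.3 points |

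The calculation is unadjusted. It gives zero when r and p are the same in both arms.

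**The case against.** The strongest reply is that the first part argues from silence. A reader might infer that EHR extraction stops at withdrawal, but no section says so, and some of the context points the other way. The trigger is missed interviews only. Aim 2 uses loss to follow-up as a pattern for participants who stay in its models. The Section 7 timeline shows EHR extraction as a periodic study-level task. The consent form is not in the reviewed text and may cover the matter. This stands, and it limits the point to what the rule says if followed as written. It does not remove the gap, because no section tells staff to keep extracting.

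A reader might also infer that the Aim 1 contrast is biased. The documents do not establish that. The GLM adjusts for the baseline outcome and other covariates, and a completers' regression remains valid if loss depends only on arm and those covariates. Bias needs loss that depends on later adherence beyond the adjusted covariates and that differs by arm.

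It is tempting to quote the undercount for any hospitalisation, using Table 5's 40%. Aim 2 reserves that form for rare events, and 40% is not rare, so those figures do not apply. Nor should 700 − 525 = 175 be taken as the number lost, since 525 is itself the figure in doubt.

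Finally, continued extraction has a weakness of its own. Records are collected by site, so a patient who has moved care elsewhere would appear to have no events. That objection is sound and shapes the fix.

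**Conclusion.** The point holds as a correction that should be made, not as a demonstrated loss of data or a demonstrated bias.

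- **Section 13.1.** As worded it would end observation early for patients silent from any of the first three follow-up interviews, and the GLMs for eGFR and hospitalisation have no rule for the result. The expected effect on the treatment comparison is small, and it rests on a constant event rate and an assumed retention gap between arms.
- **Aim 1.** Leaving out a missing-data method for the main outcome is a real gap. The illustrated error is well below the target difference, but the method would otherwise be chosen after the data are seen.
- **Analysed N.** The 525 cannot be reconciled with Aim 1's own retention rates or with the Power Calculation.

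Confidence is medium, because the sponsor may already intend to continue extraction.

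**What to change.** 1. **Section 13.1.** State that non-response ends interview attempts only. EHR outcomes are extracted to the end of the Aim 2 window unless the participant withdraws or revokes authorisation. Confirm first that the consent form covers this. For established non-responders, end the window at the scheduled date of the 2-year visit.
2. **Hospitalisation model.** End each patient's observed time at the last evidence of care at the site, so that moved care is not counted as zero events. Model the count with a log link and a follow-up-time offset; Section 11.1 names only logit and identity links.
3. **Aim 1.** Analyse all randomised patients, with multiple imputation of the 12-month adherence components. Use as predictors the baseline, 6-week and 6-month values where each is collected, plus EHR tacrolimus measures, and form the composite afterwards. Table 4 as extracted shows PDC and tacrolimus only from 6 months and pill count only at baseline and 6 months, so confirm the schedule first. Keep the completers' GLM as a sensitivity analysis.
4. **Analysed N.** Correct 525 to agree with 610.

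The cost is a short amendment, SAP wording, modest extra chart review and analysis, and possibly an IRB confirmation. Some limits remain. The EHR cannot recover self-report or pill counts. Patients who miss blood draws may lack the four levels needed for a tacrolimus SD. Imputation removes bias only as far as earlier or EHR data explain the loss.

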**14.0 Risk to Participants:**

**14.1** Participation in the study poses minimal risk of psychological, social and economic harm. Informing subjects in advance that they may decline to answer any questions asked during the interview and discussion group will mitigate any risks associated with expressing their opinions (e.g., feeling uncomfortable). They will also be assured they can terminate their participation in the study at any time without penalty. The risk/benefit ratio is low. Minimal to no risk is expected for subjects in this study.

**15.0 Potential Benefits to Participants:**

**15.1** It is possible that subjects enrolled in the intervention study arms may directly benefit in that they may have, as a result of this study, a better functional understanding of their medication. The results of this study may provide important information regarding how strategies can be implemented via the EHR and mobile and computer technologies to support safe and appropriate medication use.

**16.0 Vulnerable Populations:**

N/A

**17.0 Community-Based Participatory Research:**

N/A

**18.0 Sharing of Results with Participants:**

**18.1** Study results will not be shared with participants or anyone else.

**19.0 Setting:**

**19.1 Mayo Clinic Arizona.** The Mayo Clinic Transplant Center in the greater Phoenix, AZ area provides comprehensive evaluation, medical and surgical treatment, and follow-

up care for patients with ESRD who may be in need of a KT. The Mayo Clinic Arizona, Minnesota, and Florida campuses perform more KTs than any other institution in the U.S. At the Arizona site, they have dedicated clinical research staff involved in multiple renal transplantation clinical trials including immune-suppressive drug studies and immune monitoring trials. This infrastructure will aid [name] & [name] in conducting the study.

**19.2 Northwestern University.** Northwestern Medicine Comprehensive Transplant center (NMCTC) is the largest center for kidney transplantation in Illinois and is a leader in research, innovation and patient care in the Midwest. There are 4 satellite offices outside of Chicago, in Illinois and Indiana, to assure evaluation services closer to patients' homes. This is the largest living donor kidney transplant program in the country. It is also one of the most experienced facilities in steroid-free KT. With the Northwestern University Transplant Outcomes Research Center, led by [name], we have one of the only health services research teams in transplant.

**19.3** All in-person research interviews will take place in a private space within the study clinics at NMHC, NMCTC, and Mayo Clinic. Telephone calls with patients will also take place in a private space to ensure patient confidentiality.

**20.0 Resources Available:**

**20.1** This study is led by senior health services researchers with expertise in health literacy, medication adherence, use of EHR and consumer technologies, patient safety in transplant, and complex research designs. Additionally, the project staff have worked on similar research projects and have adequate training to carry out the proposed study.

This study is being conducted with patients from clinics within Northwestern Medical Healthcare (NMHC), Northwestern Medicine Comprehensive Transplant Center (NMCTC), and Mayo Clinic. All physicians within the practice will be informed of the study.

**21.0 Prior Approvals:**

**21.1** National Institute of Diabetes and Digestive and Kidney Disease (NIDDK)

**22.0 Recruitment Methods:**

**22.1 Identification of potential participants**

**Northwestern University**

To identify potential participants, a weekly pull of eligible patients will be reviewed by Research Coordinators (RC) at each site. At Northwestern, this report will include patient name, date of KT, phone number, address, medical record number (MRN), name of nephrologist and date of upcoming clinic visits. At Northwestern, this pull will be downloaded from the EDW. RCs will contact nephrologists to notify them about the study and to ask permission to contact all eligible patients for the study. After obtaining permission from each nephrologist to contact patients, the Director of the Kidney Transplant Program, [name] will provide written permission for RCs to contact all eligible kidney transplant recipients for the study.

